5.1.2 AE date imputation

AE end date imputation

1. If 'month' is missing, the end date will be set to the earliest of the (min (last visit date, last dose date), 31DECYYYY, and date of death).
2. If 'day' is missing, the end date will be set to the earliest of the (min (last visit date, last dose date), 31MONYYYY, and date of death).
3. If 'year' is missing or AE is ongoing, the end date will not be imputed.

AE start date imputation

Before imputing AE start date, find the AE start reference date.

- If the (imputed) AE end date is complete and the (imputed) AE end date < treatment start date then AE start reference date = min (informed consent date, earliest visit date).
- Else AE start reference date = treatment start date

After finding the AE start reference date:

1. If 'year' is missing, the date uncertainty is too high; therefore the imputed AE start date will be set to NULL.
2. If 'year' is less than the treatment start date 'year', the AE started before treatment; therefore:
 - a. If 'month' is missing, the AE start date will be set to 01JULYYYY.
 - b. If 'day' is missing, the AE start date will be set to 15 MONYYYY.
3. If 'year' is greater than the treatment start date 'year', the AE started after treatment; therefore:
 - a. If 'month' is missing, the AE start date will be set to 01JANYYYY.
 - b. IF 'month' is not missing, the AE start date will be set to the later of (01MONYYYY, AE start reference date + 1).
4. If 'year' is equal to the treatment start date 'year'
 - a. If 'month' is missing, the AE start date will be set to the AE reference start date +1.
 - b. If 'month' is less than the treatment start 'month', the AE start date will be set to 15MONYYYY.

- c. If 'month' is equal to or greater than the treatment start 'month', the AE start date will be set to the later of (01MONYYYY, AE start reference date+1).

If complete (imputed) AE end date is available and the imputed AE start date is greater than the (imputed) AE end date, imputed AE start date will be set to the (imputed) AE end date.

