5.6 Study completion and discontinuation

5.6.1 Study completion and post-study treatment

A patient will be considered to have completed the study when the patient has completed the last visit planned in the protocol.

The study as a whole will be considered completed when all randomized subjects have completed the last visit planned in the protocol (see [Table 6-1](#)) or have discontinued the study prematurely.

For subjects who are loss to follow-up, see [Section 5.6.4](#).

The investigator must provide follow-up medical care for all subjects who are prematurely withdrawn from the study, or must refer them for appropriate ongoing care.

For all patients/subjects a safety follow-up should be contacted 30 days after last visit. The information to be collected at this follow up includes concomitant medications, adverse events, and survival status.

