2.8.1.1 Adverse events of special interest / grouping of AEs

AEs of special interest, such as risks defined in the development safety profiling plan (DSPP), or topics of interest regarding signal detection or routine analysis, are defined in the electronic case retrieval sheet (eCRS) that is stored in GPS.

The pre-defined issues of special interest for LIK066 including identified risks, potential risks, and special assessments are listed below:

- Bone fractures
- Cardiotoxicity
- Diarrhea
- Electrolyte disturbances
- Genital infections
- Hepatotoxicity
- Hypersensitivity
- Hypoglycemia
- Impaired renal function
- Increased LDL

- Intravascular volume depletion
- Ketoacidosis
- Malignancy
- Pancreatitis
- Urinary tract infections
- Venothrombotic and embolic events
- Lower limb amputation
- Pre-amputation events

Treatment-emergent AEs of special interest which occur during Epoch 3 will be summarized by risk category and preferred term, by treatment. The AEs of special interest will be summarized by risk category, preferred term, treatment, and subgroups of interest (baseline glycemc status, age group, and sex) as well.

In addition, exposure-adjusted incidence rates per 100 patient years regardless of study drug relationship, by treatment will be provided by risk category and preferred term. The 95% confidence interval for the overall exposure-adjusted incidence rates per 100 patients will also be presented for each risk category, along with relative risk and 95% confidence interval.

Additional analyses for the pre-defined risks of diarrhea, ketoacidosis and hypoglycemia will be performed as described below:

Diarrhea events of special interest

Number of days with diarrhea events will be calculated for all patients with at least one incidence of diarrhea and will be summarized descriptively by treatment.

- Number of days for one diarrhea incidence = AE end date – AE start date +1.
- Number of days with diarrhea events for a patient = sum of days on diarrhea over all incidences that occurred in Epoch 3.

The number and percentage of patients with diarrhea events during the double-blind treatment period (while patients on study medication) will also be summarized by treatment over time in the following time window: 0 - <2, 2 - <4, 4 - <8, and 8 - <12 weeks.

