5.1.3 Concomitant medication date imputation

CM end date imputation

1. If 'day' is missing and 'month/year' are non-missing then impute date as the earlier of (treatment end date, and 31MONYYYY).
2. If 'day/month' are missing and 'year' is non-missing then impute date as the earlier of (treatment end date, and 31DECYYYY).
3. If imputed end date is less than the start date, use the start date as the imputed end date.

CM start date imputation

1. If 'year' is missing, the start date will be set to one day prior to treatment start date.
2. If 'year' is less than treatment start 'year', the CM started before treatment. Therefore:
 - a. If 'month' is missing, the start date will be set to 01JULYYYY.
 - b. If 'month' is non-missing, the start date will be set to 15MONYYYY.
3. If 'year' is greater than treatment start 'year', the CM started after treatment. Therefore
 - a. If 'month' is missing, the start date will be set to 01JANYYYYY.
 - b. If 'month' is non-missing, the start date will be set to 01MONYYYY.
4. If 'year' is equal to the treatment start date 'year'
 - a. If 'month' is missing or equal to the treatment start 'month', then the start date will be set to one day prior treatment start date.
 - b. If 'month' is less than the treatment start 'month', the start date will be set to 15MONYYYY.
 - c. If 'month' is greater than the treatment start 'month', the start date will be set to 01MONYYYY.

If complete (imputed) CM end date is available and the imputed CM start date is greater than the (imputed) CM end date, then imputed CM start date will be set to the (imputed) end date.

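### SAP 5.1.2 caps partial AE end dates at the last dose with no floor at the start date, so off-drug events can end before they begin or be moved into the treatment period

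*SAP*

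**What the plan says.** SAP 5.1.2 has two end-date rules.

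- Day missing: "the end date will be set to the earliest of the (min (last visit date, last dose date), 31MONYYYY, and date of death".
- Month missing: "the end date will be set to the earliest of the (min (last visit date, last dose date), 31DECYYYY, and date of death".

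It leaves some records alone: "If 'year' is missing or AE is ongoing, the end date will not be imputed".

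A partial start in the year of treatment start, with the month recorded, is handled by "If 'month' is equal to or greater than the treatment start 'month', the AE start date will be set to the later of (01MONYYYY" or the day after the start reference date. One consistency step closes the section. If the imputed start falls after the end, "imputed AE start date will be set to the (imputed) AE end date". That step acts on imputed starts only.

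The concomitant-medication rule in SAP 5.1.3 carries a guard that the AE rule lacks: "If imputed end date is less than the start date, use the start date as the imputed end date".

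AE collection continues after the last dose. Under Protocol 5.6.2, stopping drug is not study withdrawal, and AEs are still gathered at visits or by telephone. Protocol 5.6.1 adds that "a safety follow-up should be contacted 30 days after last visit", with AEs among the items collected. SAP 2.8.1 lists AEs reported after study discontinuation.

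AE dates feed the diarrhea analyses in SAP 2.8.1.1, where "Number of days for one diarrhea incidence = AE end date" minus start date plus 1, added over a subject's Epoch 3 episodes. They also feed the rule in SAP 2.8.1 that merges consecutive records of the same term when the gap is at most one day.

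**The concern.** A ceiling at the last dose suits an event that began on drug, where only on-drug days are wanted. It does not suit a general AE end date in a study that follows subjects after they stop drug. The plan then imputes an end that contradicts a recorded start, or overrides a recorded month. Diarrhea is one of the SAP's pre-defined issues of special interest, and the study is meant to support dose selection, so its day counts should not include impossible values or off-drug episodes re-dated to on-drug days.

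**Working it through.** The plan gives no figure to reproduce, so the check applies the rule literally.

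**General result.** Let L be the last dose date, S a recorded start with S ≥ L + 1, and E the imputed end. The rule forces E ≤ L. Then

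duration = E − S + 1 ≤ L − (L + 1) + 1 = 0.

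The duration is zero at best, whatever the dates.

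**Worked dates (assumed).** First dose 1 March 2018, last dose 10 April, last visit 24 May. This subject stops drug early and stays in follow-up. Each true event lasts 5 days.

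| True event | Recorded | Start used | End used | Duration |
|---|---|---|---|---|
| 15–19 Apr | full start, end day missing | 15 Apr | min(24 May, 10 Apr, 30 Apr) = 10 Apr | −4 |
| 5–9 May | full start, end day missing | 5 May | min(24 May, 10 Apr, 31 May) = 10 Apr | −24 |
| 15–19 Apr | both days missing | max(1 Apr, 2 Mar) = 1 Apr | 10 Apr | 10 |
| 5–9 May | both days missing | max(1 May, 2 Mar) = 1 May, reset to 10 Apr | 10 Apr | 1 |
| either | both months missing | 2 Mar | min(24 May, 10 Apr, 31 Dec) = 10 Apr | 40 |

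In the last three rows an off-drug event is now dated wholly on drug. In the fourth, the recorded month of May is overridden.

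**Grid check.** Assumptions: treatment starts every third day from January to June 2018 (61 dates); last dose on day 14 to 84 in weekly steps (11); onset 1 to 30 days after last dose (30); length 1, 4, 7 or 14 days (4); last visit 84 days after treatment start; end day missing. That gives 61 × 11 × 30 × 4 = 80,520 events.

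- Recorded start: the end precedes the start in all 80,520. Duration is zero in 2,684 (onset the day after last dose: 61 × 11 × 4) and negative in the other 77,836.
- Start day also missing: the start lands on the last dose date in 54% and earlier in the treatment period in 46%. This split depends on the grid.

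**Effect downstream.**

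- Diarrhea-day sum: if the first row were diarrhea, it would contribute −4 where 5 is correct, leaving the subject's total 9 days too low. This assumes that Epoch 3 runs to Week 12 for early stoppers who stay in follow-up.
- Gap rule: suppose the same term recurs on 20 April after the 15–19 April event. The true gap is 20 − 19 = 1 day, one occurrence. With the end imputed to 10 April the gap is 20 − 10 = 10 days, two occurrences.

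**The case against.** The strongest reply is that little of the safety reporting moves, and much of that stands.

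- A reader might infer that negative durations enter the negative binomial model. SAP 2.8.1.1 restricts that model to on-treatment diarrhea days, so an event with a recorded start after the last dose should not be counted. Only events with a partial start can leak in, once re-dated on drug. For an event straddling the last dose, stopping the count there is right for that endpoint.
- A reader might infer that on- and off-treatment AE tables are widely wrong. The treatment-emergent definition in SAP 2.8.1 has no upper time limit, so an off-drug event counts either way.
- A reader might infer that late events always look shorter or always move to the last treatment day. The table shows a 5-day event becoming 10 days and starting nine days before the last dose.
- A reader might take the 10% loss in the sample-size section as the exposed group, about 13 of 130. That figure concerns losses to follow-up. The exposed subjects stop drug but remain followed, and the documents give no rate for them.
- Partial end dates may be few. Protocol 7.1 asks for start and end dates or ongoing status, and Protocol 8.2 and 8.3 provide edit checks and queries.

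For completers the exposure is less certain: Protocol 7.1 ends the AE period at the end-of-study visit, while 5.6.1 collects AEs 30 days later. None of this repairs the rule itself, which yields impossible values whenever its conditions are met.

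**Conclusion.** The rule is wrong as written, with limited reach. For a recorded start after the last dose and a partial end date, a zero or negative duration is certain and rests on no assumption about dates. For both days missing, the event is moved into the treatment period: to the last dose date when its recorded month is later than the last-dose month, otherwise usually to an earlier treatment day. It can then be counted in the diarrhea time-window table and the negative binomial model.

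Only AEs with a known year, a partial end date and resolution after the last dose are affected, chiefly in early stoppers who stay in follow-up. Treatment-emergent subject counts and efficacy are largely unaffected. The number of partial dates is not given, so no overall size can be stated. It should be corrected, but it does not threaten the main conclusions.

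**What to change.** Amend SAP 5.1.2 as follows.

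1. Add the floor from SAP 5.1.3: an imputed AE end date earlier than the start date is set to the start date.
2. When the month is recorded, replace the last-dose cap with the earliest of last contact date, last day of the recorded month and death, so that neither imputed date leaves the recorded month.
3. When the month is missing, the present cap may stay, subject to the floor. Widening it to last contact would do harm: in the example, with a contact 30 days after 24 May, the span becomes 2 March to 23 June, 114 days instead of 40.
4. Truncate at last dose only within the on-treatment diarrhea analysis, not in the stored AE end date.

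On the grid, a last-contact cap plus the floor leaves 0 of 80,520 events ending before they start; the floor guarantees this by construction. The new dates are still imputed. The 15 April event with its end day missing would end on 30 April, 16 days against a true 5. If both days are missing and the recorded month is the last-dose month, on- or off-drug status cannot be settled from the data, and such events are best listed.

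The cost is a few lines of SAP text and an edit to the date-imputation macro, with no change to data collection.

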5.1.3 Concomitant medication date imputation

CM end date imputation

1. If 'day' is missing and 'month/year' are non-missing then impute date as the earlier of (treatment end date, and 31MONYYYY).
2. If 'day/month' are missing and 'year' is non-missing then impute date as the earlier of (treatment end date, and 31DECYYYY).
3. If imputed end date is less than the start date, use the start date as the imputed end date.

CM start date imputation

1. If 'year' is missing, the start date will be set to one day prior to treatment start date.
2. If 'year' is less than treatment start 'year', the CM started before treatment. Therefore:
 - a. If 'month' is missing, the start date will be set to 01JULYYYY.
 - b. If 'month' is non-missing, the start date will be set to 15MONYYYY.
3. If 'year' is greater than treatment start 'year', the CM started after treatment. Therefore
 - a. If 'month' is missing, the start date will be set to 01JANYYYYY.
 - b. If 'month' is non-missing, the start date will be set to 01MONYYYY.
4. If 'year' is equal to the treatment start date 'year'
 - a. If 'month' is missing or equal to the treatment start 'month', then the start date will be set to one day prior treatment start date.
 - b. If 'month' is less than the treatment start 'month', the start date will be set to 15MONYYYY.
 - c. If 'month' is greater than the treatment start 'month', the start date will be set to 01MONYYYY.

If complete (imputed) CM end date is available and the imputed CM start date is greater than the (imputed) CM end date, then imputed CM start date will be set to the (imputed) end date.

5.1.3.1 Prior therapies date imputation

See Section 5.1.3.

5.1.3.2 Post therapies date imputation

See Section 5.1.3.

5.1.3.3 Other imputations

Not applicable.

5.2 AEs coding/grading

AEs will be coded according to MedDRA dictionary. The MedDRA version used for reporting will be described in the footnotes. Missing severity will be assumed to be severe in the summary table.

Hypoglycemia classification is presented in [Table 5-1](#).

Table 5-1 Hypoglycemia classification

Category	Definition	Criteria as specified in the Hypo eCRF
Severe hypoglycemia	An event, requiring assistance of another person (third party assistance) to actively administer carbohydrate, glucagon, or other corrective actions, confirmed or not by a BG measurement	An event with answer = 'YES' for any one of the two questions: Was third party assistance required? Was medical assistance received?
Other clinically significant hypoglycemia	Plasma glucose < 3.0 mmol/l (54 mg/dl)* with or without typical symptoms of hypoglycaemia, and which is handled by the subject himself/herself.	An event with answer = 'YES' to the question 'Glucose measurement taken' and the plasma glucose < 3.0 mmol/l (54 mg/dl), and answer = NO to both questions: Was third party assistance required? Was medical assistance received?

*Blood glucose values need to be converted to plasma glucose values.

A plasma glucose of 3.0 mmol/L (54 mg/dL) corresponds to a whole blood glucose of 2.7 mmol/L (48 mg/dL)

Plasma glucose = blood glucose * 1.12.

5.3 Laboratory parameters derivations

5.3.1 Japanese coefficient for eGFR

The Japanese coefficient for the MDRD equation is 0.808. Therefore, eGFR with Japanese coefficient, say eGFR-J, is defined as:

$$eGFR-J = (\text{source eGFR}) \times 0.808,$$

where "source" eGFR is the one calculated by the central laboratory.

5.4 Statistical models

5.4.1 Primary analysis

See [Section 2.5.2](#).

5.4.2 Key secondary analysis

Not applicable.

5.5 Rule of exclusion criteria of analysis sets

Table 5-2 Protocol deviations that cause subjects to be excluded

Deviation ID	Description of Deviation	Exclusion in Analyses
INCL01	No written informed consent obtained	Excluded from ENR, RUN, RAN, FAS, SAF, and PPS
TRT19	Withdrawal of the consent without discontinuation of study drug	Data collected after withdrawal of IC, excluded from FAS and SAF
TRT34	Mis-randomization	Excluded from FAS and PPS
INCL03	BMI outside range or missing	Excluded from PPS
INCL04	FPG and HbA1c not within range or missing	Excluded from PPS
INCL05	Waist circumference outside range or missing	Excluded from PPS
INCL06	VFA outside range or missing	Excluded from PPS
EXCL04	Use of prohibited medications	Excluded from PPS
EXCL05	History of malignancy	Excluded from PPS
EXCL06	Pregnant or nursing	Excluded from PPS
EXCL08	Use of pharmacologically active weight-loss medications	Excluded from PPS
EXCL10	Bariatric surgery	Excluded from PPS
EXCL20	Substances or alcohol abuse	Excluded from PPS
TRT06	Study treatment adjusted	Excluded from PPS
TRT11	Study treatment unmasked and subject not discontinued from the study	Excluded from PPS
TRT15	Use of prohibited medication and not discontinued from the study	Excluded from PPS
TRT22	Use of another investigational drug	Excluded from PPS
TRT35	Study medication taken after the morning meal	Excluded from PPS
TRT28	Misdispensed medication and taken by subject	Excluded from PPS
OTH01	Mis-randomization	Excluded from PPS

Table 5-3 Subject Classification

Analysis Set	PD ID that cause subjects to be excluded	Non-PD criteria that cause subjects to be excluded
ENR	INCL01	Not having informed consent; Not having screening epoch disposition page
RUN	INCL01	Not in ENR; Not having run-in epoch disposition page
RAN	INCL01	Not randomized
FAS	INCL01, TRT19, TRT34	Not in RAN;
PPS	INCL01, INCL03, INCL04, INCL05, INCL06, EXCL04, EXCL05, EXCL06, EXCL08, EXCL10, EXCL20, TRT06, TRT11, TRT15, TRT22, TRT35, TRT 28, TRT34, and OTH01	Not in FAS; Overall exposure on DB medication < 10 weeks unless premature discontinuation due to adverse events
SAF	INCL01, TRT19	No double-blind study drug taken

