20JUL2018	Prior to DBL	Change of cut-off value for AE frequencies	Summary of the most frequent AEs includes AEs whose frequencies are $\geq 5\%$ in 50mg qd arm.	2.8.1.1 Adverse events of special interest / grouping of AEs
20JUL2018	Prior to DBL	Clarification of diarrhea event for analysis of event periods	The number of days with "on-treatment" diarrhea is used for negative binomial regression analysis.	2.8.1.1 Adverse events of special interest / grouping of AEs
20JUL2018	Prior to DBL	Project-level update on analysis plan for hypoglycemic events	It is clarified to summarize "clinically significant" hypoglycemic events. Also it is updated how to use hypoglycemic events in AE summary.	2.8.1.1 Adverse events of special interest / grouping of AEs

Date	Time point	Reason for update	Outcome for update	Section and title impacted (Current)
20JUL2018	Prior to DBL	Project-level update on the AE of special interest	“Pre-amputation events” is additionally listed as AE of special interest.	2.8.1.1 Adverse events of special interest / grouping of AEs
20JUL2018	Prior to DBL	Clarification of cut-off values for shift tables	Cut-off values are specified for selected ECG parameters.	2.8.4.1 ECG and cardiac imaging data
[REDACTED]				
20JUL2018	Prior to DBL	Documentaton of the change in analysis plan from the protocol	It is clarified which analysis to be changed from the study protocol.	4 Change to protocol specified analysis
20JUL2018	Pror to DBL	To remove confusing information about handling of hypoglycemic event data	No impact	5.2 AEs coding/grading

Date	Time point	Reason for update	Outcome for update	Section and title impacted (Current)
20JUL2018	Prior to DBL	To add PD OTH01 to handle erroneous randomization	Any patient would be excluded from PPS if randomised under a CRC's erroneous operation at the site.	5.5 Rule of exclusion criteria of analysis sets
13SEP2018	Prior to DBL	To update the units for eGFR and FPG to SI units	The units in TFLs are updated.	2.3 Patient disposition, demographics and other baseline characteristics
13SEP2018	Prior to DBL	To clarify at which time point for BW to be summarized as baseline data	It becomes clear that screening BW is to be summarized.	2.3 Patient disposition, demographics and other baseline characteristics
13SEP2018	Prior to DBL	To add categorized summary on BL eGFR with Japanese coefficients	The plan for BL summary is updated.	2.3 Patient disposition, demographics and other baseline characteristics

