2.2 Analysis sets

The following analysis sets will be used for the statistical analyses:

Enrolled set (ENR): all subjects who signed the ICF.

Randomized set (RAN): all subjects who have received a randomization number, regardless of receiving trial medication.

Run-in set (RUN): All subjects who enter the run-in epoch.

Full analysis set (FAS): the FAS comprises all subjects to whom study treatment has been assigned, except those who are not qualified for randomization but were inadvertently randomized into the study and did not take any study drug. Following the intent-to-treat principle, subjects will be analyzed according to the treatment assigned to at randomization.

Safety set (SAF): the SAF includes all subjects who received at least one dose of study medication. Subjects will be analyzed according to treatment received. Note that the safety set allows the inclusion of non-randomized subjects who received the study drug in error.

The **per-protocol set (PPS)** is a subset of the FAS. It consists of all randomized subjects in the FAS who have been exposed to study medication for at least 11 weeks, and have no major protocol deviations affecting the primary endpoint analysis.

Exposure to study medication for at least 11 weeks means that the overall duration of exposure is equal to or longer than 77 days, counted from start of randomized medication to the last intake.

Major protocol deviations will be pre-specified prior to un-blinding treatment codes for analyses.

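### SAP Tables 5-2 and 5-3 drop TRT34 subjects from the FAS without the conditions in the FAS definition, and disagree on whether TRT19 removes subjects or only later data

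*SAP*

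**What the plan says.** Protocol 9.1 and SAP 2.2 define the FAS in the same way: every subject assigned to treatment, "except those who are not qualified for randomization but were inadvertently randomized into the study and did not take any study drug". SAP 2.2 adds: "Following the intent-to-treat principle, subjects will be analyzed according to the treatment assigned to at randomization". The primary analysis uses this set (SAP 2.5.1). SAP 2.2 also states that "the SAF includes all subjects who received at least one dose of study medication".

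SAP 5.5 turns these definitions into deviation codes:

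- **TRT34**, described in Table 5-2 only as mis-randomization: "Excluded from FAS and PPS". No condition on eligibility or dosing is given.
- **OTH01**, with the identical description: excluded from the PPS only. The SAP document history says why it was added: "Any patient would be excluded from PPS if randomised under a" site coordinator's erroneous operation. Table 5-2 does not repeat that explanation.
- **TRT19**, consent withdrawn but study drug not stopped, in Table 5-2: "Data collected after withdrawal of IC, excluded from FAS and SAF".
- **Table 5-3**, in the column headed "PD ID that cause subjects to be excluded", gives for the FAS "INCL01, TRT19, TRT34", and for the SAF it gives INCL01 and TRT19.

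SAP section 4, which records departures from the protocol's analyses, mentions no change to the FAS or SAF.

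**The concern.** The tables in 5.5 are what a programmer will use to flag analysis sets. Followed literally, they do two things that the definitions in 2.2 do not allow.

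First, a randomized subject who took double-blind drug can leave the primary analysis set because of a code assigned after randomization. Which of two identically labelled codes is chosen decides whether that subject counts. An analysis described as intent-to-treat should not depend on that choice.

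Second, a treated subject who withdrew consent can lose all data from the FAS and SAF analyses, including weights and adverse events recorded while consent was in force.

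**Working it through.** **1. TRT34 and OTH01 against the FAS definition.** The definition has one exception, which needs three conditions at once. Applying each rule to the possible kinds of mis-randomized subject gives this FAS status:

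| Mis-randomized subject | Definition, SAP 2.2 | If coded TRT34 | If coded OTH01 |
|---|---|---|---|
| Ineligible, undosed | out | out | in |
| Ineligible, dosed | in | out | in |
| Eligible, undosed | in | out | in |
| Eligible, dosed | in | out | in |

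TRT34 agrees with the definition in one row of four. OTH01 agrees in the other three. Neither code is right for all mis-randomizations, so a stated criterion is needed. In the FAS row of Table 5-3 the only criterion other than deviation codes is not being in the randomized set, so the dosing condition enters nowhere. The SAF row does carry a dosing condition. A dosed TRT34 subject therefore satisfies the SAF row and fails the FAS row.

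**2. TRT19.** Table 5-2 removes data from the date of withdrawal. Table 5-3 lists the same code among those that exclude subjects, for both FAS and SAF. The SAF definition keeps anyone dosed. Protocol 5.6.3 treats data after withdrawal as missing and does not call for earlier data to be discarded. Three of the four places agree on a data cut; Table 5-3 is the odd one out.

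**3. Size.** The plan's power table is the starting point. I simulated the optimal contrast test with the six candidate shapes, group sizes 27/18/18/27/27 (placebo, 2.5, 10, 25, 50 mg; total 117), 112 degrees of freedom, one-sided 2.5% and a critical value of about 2.26:

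| Effect, SD | SAP average / minimum | Simulated average / minimum |
|---|---|---|
| 3.5%, 3% | 99.70 / 99.52% | 99.76 / 99.53% |
| 3.5%, 3.5% | 98.11 / 97.28% | 98.35 / 97.26% |
| 4.0%, 3% | 99.97 / 99.94% | 99.97 / 99.94% |
| 4.0%, 3.5% | 99.59 / 99.35% | 99.65 / 99.33% |

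The SAP's figures are reproduced. The simulation has the log-linear shape as the weakest where the SAP names the quadratic, which does not bear on this point.

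The documents give no count of TRT34 or TRT19 cases, so any loss is an assumption. For effect 3.5% and SD 3.5%:

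| Effective n | Average power | Minimum power |
|---|---|---|
| 117 | 98.4% | 97.2% |
| 112 | 98.0% | 96.7% |
| 107 | 97.6% | 96.2% |
| 104 | 97.1% | 95.5% |

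*Share of an arm.* With the planned 20 or 30 per arm (protocol 5.2), one subject is 1/20 = 5.0% or 1/30 = 3.3%.

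*Share of an imputation cell.* The imputation is fitted within treatment and stratum (SAP 2.5.3). With each stratum at 45% to 55%, a 20-subject arm has 9 to 11 per stratum, so one subject is 1/11 = 9.1% to 1/9 = 11.1% of a cell.

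*Shift in an arm mean.* If k of n subjects are dropped and they lie D points from the full arm's mean, the remaining mean moves by kD/(n − k). With assumed k of 1 to 3 and D of 2 to 4 points:

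- n = 30: from 1×2/29 = 0.07 to 3×4/27 = 0.44 points.
- n = 20: from 1×2/19 = 0.11 to 3×4/17 = 0.71 points.

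**The case against.** The best defence is that the tables are shorthand for section 2.2. TRT34 is the only code that can carry out the FAS exception, so it was probably meant for exactly those subjects, and nothing says that a table overrides the definition. The document history ties OTH01 to a site operating error, so the two codes are not wholly undistinguished. For TRT19, Table 5-2 is explicit that only later data are cut. Neither table lists TRT19 for the PPS, although INCL01 and TRT34 are listed there; that fits a data-level rule. Table 5-2's own title also speaks of excluding subjects, so the Table 5-3 column heading is weak evidence. TRT19 should also be rare, because protocol 5.6.3 requires treatment to stop at withdrawal.

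Much of this is a fair account of intent, but it does not settle the text. A site operating error is itself a way of being randomized by mistake, TRT34 is defined nowhere, and the history entry says nothing about dosing. Nor can Table 5-3 be assumed to follow 2.2: its PPS row uses less than 10 weeks of exposure with an exemption for adverse events, where 2.2 requires at least 11 weeks.

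A reader might infer more than the documents support:

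- *Every mis-randomized subject leaves the FAS.* Not so; OTH01 cases stay in.
- *Both tables delete TRT19 subjects.* Only Table 5-3 does.
- *Adverse events before withdrawal disappear altogether.* They would leave the SAF summaries, but SAP 2.8.1 still lists all adverse events in the database.

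**Conclusion.** The inconsistency is real and should be corrected. As written, TRT34 removes from the primary analysis set subjects whom the FAS definition keeps, dosed subjects above all. The tables do not say when to use TRT34 and when OTH01. Table 5-3 contradicts both Table 5-2 and the SAF definition on TRT19.

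The practical effect cannot be stated, because the number of affected subjects is unknown and may be zero. Power is not the issue: over the assumed loss of 5 to 13 effective subjects, minimum power falls by 97.2 − 95.5 = 1.7 points. The arm-mean shifts of 0.07 to 0.71 points rest entirely on assumed counts and differences. What is at stake is exclusion after randomization from an analysis called intent-to-treat, and set membership that two programmers could derive differently from the same document.

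**What to change.** Before database lock, amend SAP 5.5:

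1. **TRT34:** restrict it to subjects who meet all three conditions of the FAS definition (ineligible, randomized by mistake, no study drug taken), out of FAS and PPS. A shorter rule of mis-randomized and undosed would not do: it would drop eligible undosed subjects, whom the definition keeps.
2. **OTH01:** assign all other mis-randomizations to it, including every dosed case, out of the PPS only. State this criterion in Table 5-2 so that the two codes no longer share a bare label.
3. **TRT19:** delete it from the FAS and SAF rows of Table 5-3, or annotate it there as applying only to data after withdrawal of consent.

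The cost is rewording a few table cells and checking, blind to treatment, any deviations already coded TRT34, OTH01 or TRT19. No new data are needed. SAP 2.3.1 already provides for a listing of exclusions with reasons, which will show how many subjects were concerned.
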